8.10.5 Survival Status

To ensure current and complete survival data is available at the time of database locks, updated survival status may be requested during the course of the study by the Sponsor. For example, updated survival status may be requested before but not limited to interim and/or final analysis. On Sponsor notification, all participants who do not/will not have a scheduled study visit or study contact during the Sponsor-defined time period will be contacted for their survival status.

9 STATISTICAL ANALYSIS PLAN

This section outlines the statistical analysis strategy and procedures for the study. If, after the study has begun, changes are made to the primary and/or key objectives/endpoints or statistical methods related to those objectives/endpoints, then the protocol will be amended (consistent with ICH Guideline E9). Changes to analyses made after the protocol has been finalized, but before final database lock, will be documented in a supplemental statistical analysis plan (sSAP) and referenced in the Clinical Study Report (CSR) for the study. Post hoc exploratory analyses will be clearly identified in the CSR.

9.1 Statistical Analysis Plan Summary

Key elements of the SAP are summarized below; the comprehensive plan is provided in Sections 9.2 to 9.12.

Study Design Overview	A Multicenter, Open-label Phase 2 Study of Lenvatinib (E7080/MK-7902) Plus Pembrolizumab (MK-3475) in Previously Treated Subjects with Selected Solid Tumors (LEAP-005)
Treatment Assignment	Pembrolizumab 200 mg q3w and Lenvatinib 20 mg qd Lenvatinib 24 mg qd
Analysis Populations	Efficacy and Safety: All Participants as Treated (APaT)
Primary Endpoint(s)	1) OR per RECIST 1.1 or RANO (GBM) by investigator assessments in initial cohorts and by BICR in cohorts that expand combining the initial and expansion cohorts (Cohorts A-F). For Cohort G, OR per RECIST 1.1 by BICR assessment. 2) Safety

Key Secondary Endpoints	3) Disease control 4) DOR 5) PFS 6) OS
Statistical Methods for Key Efficacy Analysis	The point estimate and exact Clopper-Pearson confidence interval (CI) will be provided for ORR.
Statistical Methods for Key Safety Analyses	Safety will be evaluated using descriptive statistics.
Interim Analyses	For Cohorts A-F, interim analyses, based on investigator assessments of efficacy, will be performed when the first 30 participants within a tumor cohort have been followed up for approximately 6 months from study entry. The results of each IA will be reviewed by the Sponsor, and recommendations for cohort expansion will be provided. For Cohort G, an IA will be performed when the first 30 participants enrolled have been followed up approximately 6 months. The results will be reviewed by the Sponsor, and recommendations to stop or continue enrollment will be provided.
Multiplicity	No multiplicity adjustment is planned
Sample Size and Power	Cohorts A-F: Approximately 180 participants will be enrolled in the study initially; that is, 30 participants per tumor type. Based on the interim analysis, the sample size for Cohorts A, B, C, E and F may be increased to a total of 100 participants to receive pembrolizumab + lenvatinib (Arm 1). After the IA, Cohorts A (TNBC) and B (ovarian cancer) discontinued enrollment. Based on the IA, the sample size for Cohort D (CRC) may be increased to a total of 130 participants, with the first 40 after initial 30 (total 70) participants to receive pembrolizumab + lenvatinib (Arm 1) and the last 60 participants in Cohort D randomized in a 1:1 ratio to receive pembrolizumab + lenvatinib (Arm 1) or lenvatinib monotherapy (Arm 2). Cohort G will enroll a maximum of 100 participants to receive pembrolizumab + lenvatinib.

9.2 Responsibility for Analyses/In-house Blinding

The statistical analysis of the data obtained from this study will be the responsibility of the Clinical Biostatistics department of the Sponsor.

This study is being conducted as an open-label study, ie, participants, investigators, and Sponsor personnel will be aware of participant treatment assignments after each participant is enrolled and treatment is assigned. Although the study is open label, analyses or summaries generated by randomized intervention assignment, or actual intervention received will be limited and documented. Independent radiologist(s) will perform the central imaging review without knowledge of participant-level treatment status.

For Cohort D (CRC), the last 60 participants will be randomized in a 1:1 ratio between Arm 1 and Arm 2. The Sponsor will generate the randomized allocation schedule(s) for study intervention assignment for this protocol, and the randomization will be implemented in IRT.

9.3 Hypotheses/Estimation

The objectives of the study are stated in Section 3. There is no formal hypothesis for this open-label study.

9.4 Analysis Endpoints

Efficacy and safety endpoints that will be evaluated are listed below, followed by the descriptions of the derivations of selected endpoints.

9.4.1 Efficacy Endpoints

The primary efficacy endpoint is OR. For Cohorts A-F, response for the primary analysis will be determined by investigator assessments in initial cohorts and by BICR in cohorts that expand (combining the initial and expansion cohorts), with confirmatory assessment as required per RECIST 1.1 and RANO. For Cohort G, response for the primary analysis will be determined by BICR, with confirmatory assessment as required per RECIST 1.1. The ORR, defined as the proportion of participants who have a best overall response of either CR or PR using RECIST 1.1 (or RANO for GBM participants) at any time during the study, will be analyzed. Participants with unknown or missing response information will be treated as nonresponders.

Secondary Efficacy Endpoints

1. Disease control, defined as the best overall response of CR, PR, or stable disease based on RECIST 1.1.
2. DOR, defined in the subset of participants with a CR or PR, based on RECIST 1.1 (or RANO for GBM participants), as the time from first documented evidence of CR or PR until the first documented sign of disease progression or death due to any cause, whichever occurs first.
3. PFS, defined as the time from date of study treatment to the first documented disease progression based on RECIST 1.1, modified to follow a maximum of 10 target lesions and a maximum of 5 target lesions per organ (or RANO for GBM participants) or death due to any cause, whichever occurs first.
4. OS, defined as the time from the date of study treatment to the date of death due to any cause.

OR, DCR, DOR, and PFS based on iRECIST by investigator assessment are exploratory endpoints in participants who received pembrolizumab + lenvatinib combination therapy. The details on these exploratory endpoints will be provided in the supplemental SAP.

9.4.2 Safety Endpoints

A description of safety endpoint assessment is provided in Section 4.2.3.2.

The primary safety endpoints are treatment-emergent AEs, serious AEs, and discontinuation due to AEs. The AEs are graded using NCI CTCAE (Version 4.0).

Other safety endpoints include laboratory safety assessment and vital signs.

9.4.3 Patient-reported Outcome Endpoints

The PRO endpoints are based on the following questionnaires:

- EORTC QLQ-C30
- EORTC-QoL-disease-specific
 - Breast (QLQ-BR23)
 - Ovarian (QLQ-OV28)
 - Gastric (QLQ-STO22)
 - Colorectal (QLQ-CR29)
 - GBM (QLQ-BN20)
 - Biliary (QLQ-BIL21)
 - Pancreatic (QLQ-PAN26)
- EQ-5D-5L

The multi-item scales and single items (as introduced in Section 4.2.3.3) on EORTC QLQ-C30, disease-specific EORTC instruments, and on EQ-5D-5L will be summarized. The scoring algorithm of the multi-item scale(s) for each instrument will be provided in the sSAP. TTD will be evaluated for EORTC QLQ-C30 scales. Data will be summarized for pre-specified time points. Details will be provided in the sSAP.

9.5 Analysis Populations

Participants are enrolled/randomized in the study when they have received an allocation number via IRT (Section 6.3.1).

The efficacy and safety analyses populations will be defined for each tumor cohort.

9.5.1 Efficacy Analysis Populations

Efficacy Analyses will be conducted in the APaT population, which consists of all enrolled/randomized participants who received at least 1 dose of study intervention (pembrolizumab + lenvatinib combination therapy or lenvatinib monotherapy).

For the evaluation of the efficacy of pembrolizumab + lenvatinib combination therapy and lenvatinib monotherapy, the analysis population will be based on all treated participants that are allocated to the corresponding treatment arm.

The evaluation of the efficacy of the combination therapy relative to the lenvatinib monotherapy will include all treated participants from the randomized subcohort.

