1.3 Schedule of Activities (SoA)

Study Period	Screening	Intervention Period 21-Day Cycles						EOT	Post Intervention Visits			Notes
		Cycle 1		Cycle 2		Cycle 3 Onward			Safety FU ^a	Efficacy FU	Survival FU	
		1	8	15	1	15	1					
Scheduling Window (Days)		-28 to -1	±3	±3	±3	±3	±3		At DC	30 Days After Last Dose (± 7 d)	q9w ^b (± 7 d)	q12w (± 7 d)
Administrative and General Procedures												
Informed Consent	X											Consent form can be documented at any time before any protocol-specific screening procedures are performed. If the investigator plans to treat beyond disease progression, additional consent is required.
Inclusion/Exclusion Criteria	X											
Participant Identification Card	X											
Demographics	X											
Staging	X											At initial diagnosis and at study entry
Medical/Surgical History	X											

Study Period	Screening	Intervention Period 21-Day Cycles						EOT	Post Intervention Visits			Notes
		Cycle 1		Cycle 2		Cycle 3 Onward			Safety FU ^a	Efficacy FU	Survival FU	
Cycle Number/Day		1	8	15	1	15	1		30 Days After Last Dose (+ 7 d)	q9w ^b (± 7 d)	q12w (± 7 d)	
Scheduling Window (Days)	-28 to -1	±3	±3	±3	±3	±3	±3	At DC				
Prior/Concomitant Medication Review	X	X	X	X	X	X	X	X	X	X		Concomitant medications received within 30 days before the first dose of study intervention through 30 days after the last dose (or 90 days if used to treat an SAE) will be recorded.
Subsequent antineoplastic treatment									X	X	X	All anticancer therapy will be recorded until time of death or termination of survival follow-up. If a clinical visit is not feasible, follow-up information may be obtained via telephone or email.
Allocation/randomization via IRT		X										Participants will be allocated/randomized on C1D1 (-3d) after confirmation of eligibility. All procedures and assessments on C1D1 should be performed after allocation/randomization.

Study Period	Screening	Intervention Period 21-Day Cycles						EOT	Post Intervention Visits			Notes
		Cycle 1			Cycle 2		Cycle 3 Onward		Safety FU ^a	Efficacy FU	Survival FU	
		1	8	15	1	15	1		30 Days After Last Dose (+ 7 d)	q9w ^b (± 7 d)	q12w (± 7 d)	
Scheduling Window (Days)	-28 to -1	±3	±3	±3	±3	±3	At DC					

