
Objective: To evaluate disease control rate (DCR), duration of response (DOR), and progression-free survival (PFS) of pembrolizumab in combination with lenvatinib per tumor cohort based on RECIST 1.1 (RANO for GBM) by investigator assessments in initial cohorts and BICR in cohorts that expand combining the initial and expansion cohorts (Cohorts A-F). In Cohort G, RECIST 1.1 by BICR will be used in all participants.	
Disease control, defined as best overall response of CR, PR, or stable diseaseDOR, determined by disease assessment defined as the time from the earliest date of qualifying response until the earliest date of disease progression or death from any cause, whichever comes first.PFS, defined as the time from the first day of study intervention to the day of the first documentation of disease progression or death from any cause, whichever occurs first.

Objective: To evaluate overall survival (OS) of pembrolizumab in combination with lenvatinib per tumor cohort.	
OS, defined as the time from the first day of study intervention to the day of death from any cause.

Objective: To evaluate ORR, DCR, DOR, PFS, and OS of lenvatinib monotherapy (Cohort D) based on RECIST 1.1 by BICR.	
ORDCRDORPFSOS

Objective: To characterize the population pharmacokinetics (PK) of lenvatinib when coadministered with pembrolizumab in participants per tumor cohort (Cohorts A-F only).	
Plasma concentration of lenvatinib.

Objectives	Endpoints
Tertiary/Exploratory	

 Objective: To evaluate ORR, DCR, DOR, and PFS of pembrolizumab in combination with lenvatinib per tumor cohort based on iRECIST (non-GBM cohorts) by investigator assessments. 	
 OR DCR DOR PFS

 Objective: To evaluate ORR, DCR, DOR, PFS, and OS of pembrolizumab in combination with lenvatinib relative to lenvatinib monotherapy per tumor cohort. 	
 OR DCR DOR PFS OS

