Cohort D (CRC) will be expanded to include a total of 130 participants: 30 from the initial cohort and an additional 100 participants in the expansion phase. The last approximately 60 participants will be randomized 1:1 to receive pembrolizumab + lenvatinib (Arm 1) or lenvatinib monotherapy (Arm 2). The goal of this randomization is to assess the contribution of lenvatinib in the overall treatment effect of the pembrolizumab + lenvatinib combination. If a clinically meaningful response is not observed, the Sponsor may elect not to include a randomization arm and may stop enrollment.

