8.1.9 Study Intervention Administration

Pembrolizumab will be administered by the investigator and/or study staff according to the specifications within the pharmacy manual.

Study intervention should begin within 3 days of allocation/randomization.

Lenvatinib may be administered at home, except on Day 1 of Cycles 1 and 2 (required clinic visit for ECG testing, per SoA) and on Day 15 of Cycle 1 (lenvatinib PK sample collection, per SoA), for participants in Arm 1 only. Please refer to Section 8.1.9.1.1 for further details.

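### The exploratory Cohort D comparison drops anyone randomised but never dosed; comparing ORR and DCR in all randomised participants would be a cheap improvement

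*Combined protocol and SAP*

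**What the plan says.** Section 4.1.1 randomises about the last 60 Cohort D participants 1:1 to pembrolizumab plus lenvatinib (Arm 1) or lenvatinib alone (Arm 2). It gives the purpose: "The goal of this randomization is to assess the contribution of lenvatinib in the overall treatment effect of the pembrolizumab + lenvatinib combination". The matching objective in Section 3 is tertiary/exploratory: "To evaluate ORR, DCR, DOR, PFS, and OS of pembrolizumab in combination with lenvatinib relative to lenvatinib monotherapy per tumor cohort".

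For this comparison Section 9.5.1 states: "The evaluation of the efficacy of the combination therapy relative to the lenvatinib monotherapy will include all treated participants from the randomized subcohort". The efficacy population in the same section requires at least one dose. The sentence just before the quoted one, on the efficacy of each regimen, assigns treated participants by allocated arm. The comparison sentence does not repeat that rule.

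Four other places set the timing and the handling of missing data:

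- Section 9.5 counts a participant as randomised when the IRT issues the allocation number, not at first dose.
- Section 9.2 says that "participants, investigators, and Sponsor personnel will be aware of participant treatment assignments after each participant is enrolled and treatment is assigned".
- The Schedule of Activities (Section 1.3) says "Participants will be allocated/randomized on C1D1 (-3d) after confirmation of eligibility", and Section 8.1.9 says "Study intervention should begin within 3 days of allocation/randomization".
- Section 9.4.1 says "Participants with unknown or missing response information will be treated as nonresponders".

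**The concern.** Randomisation makes the two groups comparable as they were randomised. Here membership of the compared groups also depends on an event after randomisation, receipt of a first dose, when the participant and the investigator may already know the arm. The arms are visibly different: one adds an infusion, and the other is oral treatment alone. A decision not to start could therefore depend on the arm, and the treated groups would then differ for reasons other than treatment.

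This is the only randomised contrast in the study, and no hypothesis is tested (Section 9.8). The estimate and its interval are the whole output, so the denominator deserves care. No primary or secondary result is at stake.

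**Working it through.** **Does any visible rule bring undosed participants back in?** Three places were checked.

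- Section 9.5.1 restricts the comparison to treated participants.
- The nonresponder rule in Section 9.4.1 operates inside the analysis population, so it cannot restore someone whom Section 9.5.1 has removed.
- Section 9.6.3 displays the numbers enrolled/randomised and the primary reasons for discontinuation. Undosed cases can be inferred from that display, but it does not put them in the comparison.

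**Size.** The readable text gives no figure to reproduce: no undosed count, no arm-level response rates and no planned precision for this comparison. The 30 per arm follows from about 60 randomised 1:1. The rest is assumed:

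- ORR of 6/30 in Arm 1 and 2/30 in Arm 2.
- DCR of 15/30 and 12/30.
- 1 to 3 undosed participants, in one arm or in each arm.
- Miettinen-Nurminen 95% intervals. The efficacy methods text is blacked out, and in the visible text this method appears only in the reference list.

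With x responders and k undosed in an arm of 30, the all-randomised rate is x/30 and the treated-only rate is x/(30 - k). Dropping the undosed multiplies that arm's rate by 30/(30 - k). The shift is the treated-only difference (Arm 1 minus Arm 2) less the all-randomised difference.

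All-randomised reference:

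- ORR: 20.0% - 6.7% = 13.3 points (-4.6 to 32.0), width 36.7.
- DCR: 50.0% - 40.0% = 10.0 points (-15.1 to 33.9), width 49.0.

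| Undosed, then dropped | ORR difference (95% CI) | Shift | DCR difference (95% CI) | Shift |
|---|---|---|---|---|
| 1 in Arm 2 | 13.1 (-5.2 to 31.9) | -0.2 | 8.6 (-16.7 to 32.8) | -1.4 |
| 3 in Arm 2 | 12.6 (-6.6 to 31.5) | -0.7 | 5.6 (-20.1 to 30.5) | -4.4 |
| 1 in Arm 1 | 14.0 (-4.1 to 33.1) | +0.7 | 11.7 (-13.7 to 35.7) | +1.7 |
| 3 in Arm 1 | 15.6 (-3.0 to 35.5) | +2.2 | 15.6 (-10.5 to 39.6) | +5.6 |
| 1 in each arm | 13.8 (-4.7 to 33.0) | +0.5 | 10.3 (-15.3 to 34.7) | +0.3 |
| 3 in each arm | 14.8 (-4.9 to 35.0) | +1.5 | 11.1 (-15.5 to 36.2) | +1.1 |

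Worked example, DCR with 3 undosed in Arm 2: 15/30 - 12/27 = 50.0 - 44.4 = 5.6 points, against 10.0 with all randomised.

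Loss from Arm 2 shrinks the apparent advantage of the combination, and loss from Arm 1 inflates it. One-sided loss moves DCR more than ORR because its rates are higher. With k = 0 in both arms the two analyses are identical.

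**The case against.** The strongest reply is that this hardly matters. The comparison is tertiary (Sections 3 and 4.1), nothing is tested, and every shift above lies well inside its interval. The larger DCR shifts need wholly one-sided loss of up to 3 in 30, which the documents do not show. The opportunity is also narrow: eligibility is confirmed before randomisation, and the schedule is compatible with randomising and dosing on the same day. The 3 days are an outer allowance, although Section 8.1.9 says only that dosing should begin by then. All of this stands, and it limits the point to an optional improvement.

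Estimating the effect among treated participants is also a defensible choice in a proof-of-concept study, and counting undosed people as nonresponders is a convention that adds no information on drug effect. That is a reason to keep the treated analysis as a companion. It does not restore the comparability given up by an exclusion made with the arm known.

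Consistency is a further objection. The quoted sentence also governs PFS and OS, so changing only ORR and DCR puts one objective on two populations. That is a real cost. It is accepted because PFS and OS are defined from first dose and the imaging schedule runs from treatment initiation (Section 8.2.1.2), so an undosed participant has no time origin under those definitions.

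A reader might infer that the plan analyses participants by treatment received, or that it contains no all-randomised analysis at all. Neither is supported. The as-received rule is in Section 9.5.2, for safety. The efficacy methods text is blacked out and the supplemental SAP is not available, so an all-randomised sensitivity analysis cannot be ruled out.

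**Conclusion.** The point holds as a low-priority improvement. On the visible text, a participant randomised in Cohort D but never dosed is left out of the combination-versus-monotherapy comparison, and the arm can be known before that happens. On the assumed counts the effect is at most 2.2 points for ORR and 5.6 points for DCR, against intervals about 37 and 49 points wide. It is about 1.5 points or less on either endpoint if losses are equal, and zero if everyone is dosed.

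A reader might go further and conclude that the comparison is biased. The documents do not support that: they give no undosed rate and no evidence that non-dosing differs by arm. Nor does the point reach the primary ORR analyses, the secondary single-arm results or the safety summaries.

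**What to change.** For the Cohort D combination-versus-monotherapy comparison only:

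1. State in Section 9.5.1 that ORR and DCR are compared in all randomised participants by assigned arm. This also puts the arm rule in the comparison sentence itself.
2. Count undosed participants as nonresponders and as not having disease control, extending the Section 9.4.1 rule.
3. Keep the treated set as the companion sensitivity analysis.
4. Show the number randomised but undosed, by arm, which makes explicit what the Section 9.6.3 disposition display gives only indirectly.

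Keep PFS and OS in treated participants from first dose, and say that the comparison therefore uses two populations. DOR is defined in responders only and is unaffected. Leave the secondary single-arm analyses and the safety summaries on the treated population.

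The cost is SAP wording and one table; the assignment is already in the IRT, and no extra participants or visits are needed. There are two downsides. The ORR and DCR rates are slightly diluted if anyone goes undosed. Also, every Arm 2 participant belongs to the randomised subcohort, so a single undosed Arm 2 participant would give Arm 2 one ORR and DCR denominator as a secondary result (treated) and another in the comparison (all randomised). The tables must label which is which.

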9.5.2 Safety Analysis Populations

Safety Analyses will be conducted in the APaT population, which consists of all enrolled/randomized participants who received at least 1 dose of study intervention (pembrolizumab + lenvatinib combination therapy or lenvatinib monotherapy).

In the APaT population for safety analysis, participants will be included in the treatment arm corresponding to the study intervention that they actually received. For most participants, this will be the treatment arm to which they are randomized. Participants who take incorrect study intervention for the entire treatment period will be included in the treatment arm corresponding to the study intervention actually received.

At least 1 laboratory, vital sign, or ECG measurement obtained after at least 1 dose of study intervention is required for inclusion in the analysis of the respective safety parameter. To assess change from baseline, a baseline measurement is also required.

[figure not shown]
